Inferior Alveolar Nerve Lateralization and Immediate Dental Implant Placement in Severely
Resorbed Mandibles: A Clinical Trial

14/6/2024

NCT not assigned yet

Inferior Alveolar Nerve Lateralization and Immediate Dental Implant Placement in Severely Resorbed Mandibles: A Clinical Trial

Background:

Alveolar bone resorption is initiated following tooth extraction or loss as a consequence of diminished mechanical loading and disruption of the physiologic bone remodeling balance, leading to progressive atrophy of the residual ridge. Significant interindividual variability as well as intraindividual variations over time and across various regions of the residual ridge are observed in the rate and extent of alveolar bone resorption after tooth loss [1].

A recent systematic review evaluated the dimensional changes in the hard and soft tissues of the alveolar process up to 12 months following tooth extraction [2]. Because of anatomical and biomechanical differences, the maxilla and mandible show different patterns and magnitudes of alveolar bone resorption after tooth loss. Studies have shown that bone loss in the maxilla usually happens more quickly, with an average vertical reduction of 1.5–2 mm in the first six months and up to 40–60% of ridge width over the course of three to five years. On the other hand, cortical bone resorption in the mandible is typically slower but more noticeable, especially in the anterior region, where height loss can reach 4-5 mm in the first year. Nonetheless, there is a great deal of variation based on variables like systemic health, periodontal phenotype, and occlusal forces. Because the buccal bone plates in the posterior regions of both jaws are thinner, they tend to resorb more quickly, whereas the mandibular anterior ridge, supported by dense cortical bone, often retains greater residual volume [3].

The mechanism of bone resorption that occurs after tooth loss has been fully understood; it is explained as the organic components of intracellular substance being removed by proteolytic action of osteoclasts. On the other hand, the inorganic salts are dissolved by the chelating action of osteoclasts as resorption takes place. The osteocytes released may revert back to osteoblasts or osteoclasts depending upon physiologic and pathologic demands [4]. Residual ridge

resorption (RRR) may continue beyond the alveolar bone to affect the basal bone of the upper and lower jaws, sometimes leaving only a thin cortical plate on the inferior border of the mandible or virtually no maxillary alveolar process on the upper jaw. In the lower jaw, a knife-edge ridge might result from severe buccolingual resorption that may be masked by redundant or inflamed soft tissue, which can be detected by palpation or by lateral cephalometric radiographs [4].

Several classification systems have been proposed to describe the extent and pattern of mandibular ridge resorption. Atwood's [1], Cawood and Howell's [5], Lekholm and Zarb's Classification [6], and Seibert's Classification [7]. Cawood and Howell's classification is the most widely used classification in general assessment in dental implantology and describes six stages of ridge resorption: Class I: Dentate ridge, Class II: Immediately post-extraction, Class III: Well-rounded ridge (favorable for dentures), Class IV: Knife-edged ridge (reduced width), Class V: Flat ridge (loss of height and width), and Class VI: Depressed ridge (severe resorption with basal bone loss) [5].

RRR is a multifactorial biomechanical disease that results from a combination of anatomic, mechanical, and metabolic determinants [8-10]. The mandible ridge undergoes resorption largely from the occlusal plane due to the mandible's greater width at the inferior border compared to the remnant alveolar ridge in the posterior region of the mouth. The resorption action increasingly separates the left and right ridges. Consequently, RRR is centripetal in the maxilla and centrifugal in the mandible [4]. Tallgren, Atwood, and Coy [11, 12] found the mean ratio of anterior maxillary to anterior mandibular RRR was 1:4. Therefore, on average, RRR is greater in the mandible than in the maxilla.

The placement of implants in severely resorbed posterior mandibles (Cawood-Howell categorization classes V and VI) is problematic due to inadequate bone volume, reduced attached and unattached mucosa, and the superficial positioning of the inferior alveolar nerve

[13]. Numerous therapeutic modalities have been suggested in the literature to tackle this issue, including the insertion of short implants, sandwich osteotomy, vertical ridge augmentation, and distraction osteogenesis. An alternative approach involves exposing the Inferior Alveolar Nerve (IAN) by laterally displacing it from the canal through nerve lateralization or transposition [14, 15].

The inferior alveolar nerve, a major branch of the mandibular nerve, innervates the mandibular teeth, periodontium, lower lip, and jaw. It traverses the lower jaw via the mandibular foramen, encased in firmly bound connective tissue, and subsequently proceeds downward and forward within the mandibular canal, typically situated behind the root apex [13]. Within the mandibular canal, it accompanies the inferior alveolar artery (IAA), vein, and lymphatic vessels, forming the inferior alveolar neurovascular bundle [16, 17]. The assessment of the infra-alveolar nerve canal's relative position and its association with mandibular anatomical landmarks can be therapeutically advantageous in reducing the risk of surgical problems, such as nerve damage, that may arise following invasive mandibular surgeries. Furthermore, the evaluation of bone height and width includes the Cone Beam Computed Tomography (CBCT) study of the trajectory and location of the mandibular canal [18].

Two techniques pertain to the alveolar nerve; the initial technique involves inferior alveolar nerve transposition (IANT) via a bone window fashioned in the cortical bone of the jaw, posterior to the mental foramen, excluding it. The second approach incorporates the mental foramen inside the established bone window and is referred to as IANL [19, 20]. In contrast to graft-based reconstruction methods, the lateralization procedure eliminates the need for donor sites, thereby reducing patient morbidity, lowering expenses, facilitating the immediate placement of long implants (as it utilizes all available jawbone), and averting a six- to eight-month waiting period for treatment [21]. IAN lateralization is a complex surgical operation that necessitates the exposure of the neurovascular bundle from its dense bone compartment and sufficient retraction, with the prompt implantation of an implant. This operation necessitates

substantial clinical expertise, anatomical understanding, and the capability to address any complications [22-25].

Varying methods of IANL and immediate implant placements that have used drills, burs, or saws have been reported [26, 27]. Disturbances in postoperative neurosensory function of the IAN are common. The risk of IAN morbidity created some controversy, which resulted in the limited use of this classic technique [28]. To tackle problems in edentulous instances, especially those with atrophic mandibles, various surgical procedures utilizing osseointegrated implants have been devised [29]. Onlay bone grafting, a prevalent approach, necessitates a secondary surgical site and entails hazards including graft resorption, infection, and the requirement for two surgical procedures, thereby prolonging the entire treatment duration [29-31]. The bone quality in the posterior mandible is generally lower than that of the anterior area. Utilizing short implants to circumvent the mandibular canal often results in initial implant anchorage that is monocortical and comparatively unstable [32].

The key benefits of IAN relocation encompass the utilization of standard-length implants with bicortical anchorage, hence augmenting primary stability, which is essential for effective osseointegration. Implants accompanied by nerve relocation have a reduced risk of bone loss when compared to short implants implanted under analogous conditions [33]. In instances when the vertical bone height is below 5 mm—insufficient for even small implants—IAN repositioning is the advised procedure [34]. This treatment enhances resistance to occlusal stresses and guarantees an appropriate implant-to-prosthesis connection. In comparison to bone grafting, IAN relocation presents multiple advantages: it can be executed under local anesthetic, eliminates the need for a donor site, incurs cheaper expenses, and is linked to diminished morbidity [14, 35]. The present study aimed to investigate the efficacy of the IANL procedure for dental implants in the atrophied mandibles.

Patients and Methods:

This is a prospective randomized clinical trial. The study was carried out in patients with posterior mandibular atrophies among selected cases from patients attending Faculty of Dentistry dental polyclinics and some private dental clinics in Sana'a City from 10 July 2024 to 20 April 2025. The minimal calculated sample size was nine cases (G-power sample calculator; Effect size, 99.99; α err prob, 0.05; Power, 0.80; and Df, 7) [36]. The age of patients was above 18 years, according to [36]. Patients included in the study were those who have a bone height above the IAN that ranged from 0.5 to 7.0 mm and patients with bone width less than 5 mm in the planned dental implant sites. All patients were informed about alternative treatments and given information regarding all steps of the procedure, the risks of the surgery, and possible postoperative neurosensory dysfunction. All explanations were given to the patients verbally and in a written manner. Patients with active infections, uncontrolled diabetes, or a history of radiotherapy, chemotherapy, or oral cancer surgery were excluded from this study. Demographic data (name, age, gender, occupation, address, phone number, and habits) were collected using a preformed questionnaire. Present and past medical and dental history was also recorded for all patients. All patients received a thorough dental examination (extra-oral and intra-oral examination) in dental clinics using a dental mirror, ball-tipped WHO dental probe, and dental tweezers. Sterile examination tools by autoclave class B were used. Clinical examination included oral health and oral hygiene status, interarchdistance, dimensions of edentulous ridge, and soft tissue condition. Panoramic radiographs were taken to assess the condition of the patients' teeth and jawbone, as well as to detect any oral infections requiring treatment. These images also served as baseline documentation for comparison before and after treatment. CBCT revealed significant vertical and horizontal bone loss (bone quantity) and bone density (bone quality) in the mandibular premolar and molar areas, with the residual bone above the IAN ranging from 0.5 to 7.0 mm. All cases' mandibles were classified as class V (flat ridge form, inadequate in height and width) or class VI (depressed ridge form, with some basilar loss evident) according to the Howell-Cawood classification [5]. All patients were provided written

informed consent and received a modified questionnaire of that proposed by Hashemi to register any ND and success rate of dental implant after the operation [37].

Surgical protocol:

At the outset, both the patients and instruments were prepared for the procedure. The surgical setup included dental examination instruments, an anesthesia kit (stainless-steel syringe, needle, and anesthesia cartridge), a scalpel with a No. 15 blade, a periosteal elevator, a Minnesota retractor, a piezoelectric device (Mectron Piezosurgery Device, Mectron) with burs, elastic tape for nerve lateralization, a Woodpecker dental implant device, AnyRidge MegaGen dental implants, a centrifuge with tubes and resorbable collagen membrane, 3/0 suture material, and a complete set of sterilization instruments. Local anesthesia was administered using lidocaine with adrenaline at a concentration of 1:80,000. A 27-gauge long needle was used with a stainless-steel syringe to perform IAN, lingual nerve, and long buccal nerve blocks. A triangular mucoperiosteal flap was performed; a crestal incision as well as an envelope with vertical releasing incision began from the retromolar region and was carried forward to the distal for the canine. A scalpel and blade were used to expose the alveolar crest and lateral body of the mandible of the posterior area. Then the mucoperiosteal flap was reflected by a periosteal elevator, and the mental nerve was then identified and relieved from the underlying tissue to free the mucoperiosteal flap during reflection, and then all flaps were reflected by a Minnesota retractor.

Piezoelectric osteotomy:

For the purpose of inferior alveolar nerve lateralization, a linear occlusal cortical osteotomy was performed with a piezoelectric device (Mectron Piezosurgery Device, Mectron) by Piezosurgery osteotomy burs from the prepared implant bed into a medial and distal direction, extending 3–4 mm in length bilaterally, with a depth compatible with the existing thickness of the cortical bone [38].

The osteotomy separates the implant bed into 2 relatively equal parts. Subsequently, anterior and posterior vertical osteotomies (8–15 mm in length) are performed on the buccal surface of the mandible with the piezoelectric device to a depth compatible with the thickness of the cortical bone. A horizontal osteotomy is then performed with the piezoelectric device at the apical level to unite the vertical osteotomies and define a square bone window [38].

Nerve lateralization:

The cortical bone block is removed with the aid of a periosteal elevator and kept hydrated in saline solution. After osteotomy, the mandibular canal is exposed, and the IAN is gently manipulated to remove cancellous bone fragments that may hinder a full mobilization of the IAN. The nerve was retracted laterally by a specially fabricated instrument (elastic tape), according to [39], and carefully protected in a way to allow implant bed preparation through its medial surface up to the desired bone depth.

Implant placement:

The AnyRidge MegaGen dental implants were then inserted to the ideal locking depth, in accordance with the predetermined position and direction. The selected implants should be long enough to allow anchorage in the basal cortical bone of the mandibular body and provide adequate locking and stability [38].

Inlay autogenous bone graft repositioned:

The inner surface of the previously harvested bone block can be contoured using specialized piezoelectric tips to ensure precise adaptation to the defect site at the end of the surgery, promoting close bone-to-implant contact. This approach results in an optimal inlay autogenous bone graft, which is the basis for the technique's name. The bone block is then repositioned and secured in its original location to effectively close the bone defect [38]. In the final step, soft tissues were carefully approximated and sutured using interrupted stitches with 3-0 silk sutures.

Post-operative care:

Patients received standard postoperative care instructions and were advised to avoid chewing on the operated side. A soft and liquid diet was recommended during the implant osseointegration period. Anti-inflammatory drugs, analgesics, and antibiotics were administered according to established protocols. Neurostimulatory drugs (methylcobalamin) can be administered shortly after surgery, depending on the patient's sensory perception and the IAN trauma extension. Sutures are removed only after confirmation of edge repair, usually 12 days after surgery. Implants are loaded 90 to 120 days after insertion [38].

Post-operative follow-up:

Testing of nerve function and implant success rate during the scheduled follow-up visits was scheduled on the day after the procedure and at 1, 3, and 6 months immediately following the surgery [40]. Patients were asked about pain and neurosensory disturbance classified as positive (including paresthesia, dysesthesia, and hyperesthesia) or negative (such as hypoesthesia and anesthesia). The incidence and duration of neurosensory disturbance were evaluated by the light touch test using cotton or gauze. A cotton tip applicator is used to determine sensation (Static Touch Detection Tests), and a pinprick test is done with an insulin needle and the tip of an explorer probe at predetermined intervals of time. Neurosensory evaluation was carried out on the 1st and 7th postoperative days and every month thereafter for up to 6 months. The areas of impaired nerve function were mapped and followed during each follow-up appointment. The evaluation of nerve function was performed by two calibrated examiners. [34] The implant success rate was done by primary stability during insertion by ratchet, then X-rays (panorama and CBCT) were taken at 3 months and 4 months after implant insertion to check for marginal bone loss (MBL). The degree of osseointegration of the implants was determined by examining whether or not the implants were both painless and immobile when under torque and while

loading and whether or not any pathology was detected in the X-rays during the examination [34].

Abutments and prosthodontic procedures:

In this study, all patients received prosthetic rehabilitation using AnyRidge (MegaGen) implants with multi-unit abutments to ensure a predictable and efficient restorative phase. The multi-unit abutments, designed by the manufacturer, were selected based on implant angulation and soft tissue thickness, with both straight and angled options (15° and 25°) and various collar heights available to accommodate individual anatomical variations. These abutments helped standardize the prosthetic platform, simplify the restoration delivery, and improve long-term outcomes. All prostheses were cement-retained, except for one case where a screw-retained restoration was employed. The use of multi-unit abutments played a key role in managing implant angulation and facilitating a smooth and accurate prosthodontic alignment.

Data management and statistical analysis:

All data were collected and then analyzed using statistical software (SPSS Version 27; SPSS Inc., Chicago, USA). Descriptive analyses were performed as frequency and proportion for categorical variables and the mean and standard deviation of quantitative variables. Analytical statistics were performed to find out the association between variables (demographic characteristics, neurosensory disturbance, and success rate of implant) with IANL. Non-parametric tests were done to measure the differences between pre- and post-times of operation (Fridman and Wilcoxon tests). $P < 0.05$ was considered statistically significant.

List of Abbreviations:

Abbreviations

Definition

IAN

Inferior Alveolar Nerve

IANL

Inferior Alveolar Nerve Lateralization

IANT

Inferior Alveolar Nerve Transposition

RRR

Residual Ridge Resorption

CBCT

Cone Beam Computed Tomography

ND

Neurosensory Disturbances

MC

Mandibular Canal

PRF

Platelet-Rich Fibrin

MBL

Marginal Bone Loss

Declarations:

Ethics approval and consent to participate: The study design adhered to the tenets of the Declaration of Helsinki and was approved by the Medical Research Ethics Committee in the Faculty of Medicine at Sana'a University; ethical approval was obtained (Approval Number: OMFS:14/06/2024). Detailed explanation of the procedures was provided for all participants. Verbal and written consent were obtained from all participants; all patients agreed to be involved in the study.

Clinical trial number: not applicable.

Consent for publication: NA

Availability of data and materials: The authors confirmed that the raw data that support the findings of this study are available from the corresponding author upon reasonable request.

Competing interests: The authors declare that they have no competing interests.

Funding: The study was self-funded by the authors.

Authors' contributions: HS & YA performed the surgical interventions and collected data from the patients and drafted the manuscript. MA performed the conceptualization of the study and was a major contributor in writing the manuscript. YA, AA, and TA revised the clinical work and the draft manuscript. All authors read and approved the final manuscript.

Acknowledgements: the authors thank all the patients included in the study as well as the Department of Oral and Maxillofacial Surgery in the Faculty of Dentistry, Sana'a University.

References:

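### The study is labelled randomized, but the plan describes one IANL pathway with no second arm, comparator, allocation or between-group test

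*Combined protocol and SAP*

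**What the plan says.** The combined protocol and SAP opens Patients and Methods with the design statement "This is a prospective randomized clinical trial". Outside the reference list, this is the only place where the study is called randomized; the title says only that it is a clinical trial.

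The rest of the plan reads as follows.

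- **Aim (end of Background):** the efficacy of IANL for implants in atrophied mandibles, with no comparator.
- **Sample size (Patients and Methods):** a minimum of nine cases in total, from effect size 99.99, alpha 0.05, power 0.80 and Df 7. No per-arm number or ratio is given.
- **Alternatives:** in the methods they appear only as patient information: "All patients were informed about alternative treatments".
- **Treatment (Surgical protocol to Post-operative care):** one sequence of piezoelectric osteotomy, nerve lateralization, implant placement, repositioned bone block and aftercare. Under Abutments and prosthodontic procedures, "all patients received prosthetic rehabilitation using AnyRidge (MegaGen) implants with multi-unit abutments".
- **Analysis (Data management and statistical analysis):** descriptive statistics, then "Analytical statistics were performed to find out the association between variables (demographic characteristics, neurosensory disturbance, and success rate of implant) with IANL", then Friedman and Wilcoxon tests of differences between times before and after the operation, with no outcome named.
- **Neurosensory assessment:** a questionnaire is used "to register any ND and success rate of dental implant after the operation". Post-operative follow-up gives two schedules: "scheduled on the day after the procedure and at 1, 3, and 6 months immediately following the surgery" and "Neurosensory evaluation was carried out on the 1st and 7th postoperative days and every month thereafter for up to 6 months".

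**The concern.** Readers take the word randomized to mean that patients were allocated by chance between at least two conditions, so that a difference between groups is protected from selection bias. The plan describes no groups and hence no such difference. If the label stands, single-group results may be read, cited or pooled as randomized evidence that IANL works better than something else. What the described design can support is narrower: proportions in one treated group, and change within patients over time.

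Two sentences in the analysis section share the mismatch in a milder form. An association with IANL cannot be estimated when every patient described has IANL. The before-and-after tests name no outcome, and for neurosensory disturbance no preoperative test is described.

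**Working it through.** **1. What a randomized design needs, set against what the plan contains**

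| Element | Where it would stand | What is there |
|---|---|---|
| Comparator | Aim; Patients and Methods | None. Short implants, grafting, sandwich osteotomy, distraction and nerve transposition appear only in Background |
| Allocation sequence, ratio, concealment | Patients and Methods | None. Cases are selected from clinic attenders and no allocation step follows |
| Per-arm sample size | Patients and Methods | None. One total of nine |
| A second treatment | Surgical protocol to Abutments | None. One pathway |
| Between-group test | Data management and statistical analysis | None. Friedman and Wilcoxon are used on time points |

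Some care varies between patients: abutment type by implant angulation and soft tissue, a neurostimulatory drug by sensory findings and extent of nerve trauma, and one screw-retained prosthesis. None of this is presented as allocated. The design, surgical, follow-up and analysis sections are all present and read continuously, so removed pages do not explain the gap.

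**2. Does the sample-size statement imply two groups?**

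The stated nine was checked first, trying several tests because the plan names none.

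- Two means, two-sided: n per arm = 2(1.960 + 0.842)² / 99.99² = 15.70 / 9998 = 0.0016, which rounds up to 1. A two-sample t-test with 2 + 2 patients already has power of about 1.00.
- Chi-square with Df 7: the noncentrality for 80% power is 14.35, so N = 14.35 / 99.99² = 0.0014.
- F test with 7 numerator df (eight groups): nine is the smallest N that leaves a residual degree of freedom. Power there is about 1.00 if 99.99 is f. If 99.99 is f², power is 0.54 at N = 9 and 0.999 at N = 10.

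Nine therefore appears only as the floor of an eight-group design, never as the size that gives 80% power. That is a separate defect, but it means that the calculation cannot be used to recover the design.

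Df 7 is also ambiguous:

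- two-group t-test on nine cases: 9 − 2 = 7;
- correlation or simple regression on nine cases: 9 − 2 = 7;
- Friedman test across the eight visits of the second schedule: 8 − 1 = 7.

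The last of these is a within-patient test. Df 7 does not establish a second arm.

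**3. Other possible traces of an arm**

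The surgical kit lists a centrifuge with tubes, and the List of Abbreviations defines PRF (platelet-rich fibrin). No PRF step, group or comparison is described anywhere in the methods.

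**4. Neurosensory assessments by time**

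- First schedule: 1 (day after surgery) + 3 (months 1, 3 and 6) = 4, all postoperative.
- Second schedule: 2 (days 1 and 7) + 6 (months 1 to 6) = 8, all postoperative.
- Preoperative neurosensory tests described: 0. The clinical examination listed in Patients and Methods includes no sensory test.

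**The case against.** The strongest objection is that the documents do not settle which half is wrong, the label or the description. The centrifuge, the PRF abbreviation and Df 7 could be remnants of a comparison that was never written up. This stands in part. None of the three defines an arm, but together they are reason to ask a neutral question before the label is replaced. A reader might infer either that the authors certainly randomized nobody, or that there was a hidden PRF arm. The documents support neither inference; they show only that the label has no support in the text.

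The shared implant system is weak evidence of a single arm, because randomized arms can share an implant. That is correct, and the conclusion does not rest on it.

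The harm can also be overstated. The title does not say randomized, the aim names no comparator and the named tests are within-patient. A reader might infer that an invalid between-group analysis is planned. None is; the risk is a misleading label and what others build on it.

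Finally, a reader might infer that the before-and-after tests have no baseline at all. The documents do not support that. Of the radiographs the plan says "These images also served as baseline documentation for comparison before and after treatment", and preoperative ridge dimensions, soft tissue and history are also recorded. In the questionnaire sentence, the phrase about timing may qualify only implant success, and the instrument itself is not shown. What stands is narrower: no preoperative neurosensory test is described.

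**Conclusion.** The point holds. The stated design property is unsupported by the rest of the plan: one pathway, one total of nine cases, no comparator, no allocation method or ratio, and no between-group test. As described, the study can yield single-group proportions and within-patient change, but no randomized or comparative conclusion on efficacy. The label conflict must be fixed. Its size is a matter of what is present or absent in the text, and no p-value or interval would measure it.

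The wording of the association sentence and the unnamed outcome for Friedman and Wilcoxon are secondary specification points. They do not carry the same weight. The association sentence has a sensible reading, namely associations among IANL-treated patients, that only needs to be stated.

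The verdict assumes that the methods text is complete as it stands. If an allocation took place and was left out, the plan is still deficient, because the arms, the method and the between-group analysis are then missing.

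**What to change.** **Main change**

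1. State whether patients or sites were allocated to anything. Explain the centrifuge and tubes, the PRF abbreviation, and the test to which Df 7 belongs.
2. If nothing was allocated, call the study a prospective single-arm study. Limit conclusions to single-group proportions and within-patient change, with no randomized or comparative claim of efficacy.
3. If allocation did occur, describe the arms, the allocation method and the between-group analysis.

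**Lower priority**

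4. Reword the association sentence so that it refers to associations among IANL-treated patients.
5. Name the outcome for the Friedman and Wilcoxon tests. For neurosensory disturbance, call them tests of change across postoperative visits, unless a preoperative assessment was recorded.

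**Cost.** If nothing was allocated, these are wording changes in the design and analysis sections. The randomized label is lost, and for neurosensory disturbance the before-and-after wording narrows unless a baseline exists. No new patients or data are needed. If allocation did occur, the authors have the larger task of writing up the arms, the method and the comparison.

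### The printed sample-size inputs (effect size 99.99, power 0.80, Df 7) do not yield nine cases for the planned Friedman and Wilcoxon tests; nine returns only under readings the text does not state

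*Combined protocol and SAP*

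**What the plan says.** The Patients and Methods section gives the whole justification in one sentence: "The minimal calculated sample size was nine cases (G-power sample calculator; Effect size, 99.99; α err prob, 0.05; Power, 0.80; and Df, 7", followed by a citation to reference 36. It names no test, outcome, effect-size metric or sidedness, and does not say what Df refers to.

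The only tests named anywhere are in the Data management and statistical analysis section: "Non-parametric tests were done to measure the differences between pre- and post-times of operation (Fridman and Wilcoxon tests". The same section says "Descriptive analyses were performed as frequency and proportion for categorical variables", and sets a significance threshold of 0.05 without saying whether tests are one- or two-sided. It also plans unspecified analyses of association.

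The Post-operative follow-up section treats the nerve outcome as categories: "neurosensory disturbance classified as positive (including paresthesia, dysesthesia, and hyperesthesia) or negative (such as hypoesthesia and anesthesia". It gives two timetables. One is "Neurosensory evaluation was carried out on the 1st and 7th postoperative days and every month thereafter for up to 6 months", which makes eight post-operative visits. The other is "scheduled on the day after the procedure and at 1, 3, and 6 months immediately following the surgery", which makes four.

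**The concern.** A standardised effect of 99.99 means a shift of about one hundred standard deviations. At that size power cannot be the quantity that sets the sample size: any test that can reach significance at all will do so. A power of 0.80 at nine cases is therefore not a result that these inputs can produce for the planned tests.

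This sentence is the plan's only basis for its minimum size and its only power claim. As it stands, a reader cannot tell which effect, outcome or test nine cases were meant to serve, or whether the 0.80 would survive two-sided testing.

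**Working it through.** **Inputs.** N = 9, effect 99.99, alpha 0.05, power 0.80, Df 7 (Patients and Methods); Friedman and Wilcoxon tests (Data management and statistical analysis); eight or four post-operative visits (Post-operative follow-up). Sidedness is not stated, so both were tried.

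**Step 1: effect 99.99 as printed, planned tests.**
- Paired t: noncentrality = effect × √n. At n = 2 this is 99.99 × 1.414 = 141.4, and power is about 1.00. Needed N: 2.
- Exact Wilcoxon: the limit is the smallest attainable p. One-sided this is 1/2^n: 0.0625 at n = 4, 0.031 at n = 5. Two-sided it is 2/2^n: 0.0625 at n = 5, 0.031 at n = 6. Needed N: 5 or 6.
- Friedman, k = 8 visits, chi-square approximation, df 7, critical value 14.07. If every patient orders the visits identically, the statistic is n(k − 1): 14 at n = 2 and 21 at n = 3, so N = 3. If one visit is shifted and the others are exchangeable, simulated power is 0.15 at n = 3, 0.44 at n = 4 and 0.82 at n = 5, so N = 5. Adding baseline to the one-shift pattern (nine times, df 8) gives 0.76 at n = 5 and 0.99 at n = 6, so N = 6.

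Every result is below nine, and power at nine is about 1.00.

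**Step 2: what Df 7 could mean.** It fits eight visits without baseline (8 − 1), eight pairs (8 − 1), or nine cases with N − 2. It does not fit nine pairs (df 8), eight visits plus baseline (df 8), or the four-visit timetable (df 3, or 4 with baseline). A generic chi-square with df 7 needs a noncentrality of 14.35. That gives N = 14.35/99.99² = 0.0014, i.e. 1; at 0.9999 it gives 14.35/0.9998, i.e. 15.

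**Step 3: readings that do return nine.**
- *Effect 0.9999, one-sided matched-pairs Wilcoxon.* The t approximation uses n × ARE (asymptotic relative efficiency) in place of n, with df = n × ARE − 1.

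| ARE | Power, n = 8 | Power, n = 9 | df, n = 9 |
|---|---|---|---|
| 0.864 (minimum) | 0.748 | 0.803 | 9 × 0.864 − 1 = 6.78 |
| 0.955 (normal) | 0.795 | 0.844 | 9 × 0.955 − 1 = 7.59 |

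  Nine is the first N to reach 0.80 in both rows. A one-sided paired t at 0.9999 gives eight instead (power 0.815, df 7).
- *F-test with eight groups, f = 99.99.* At N = 9 the df are 7 and 1, the critical F is 236.8, and lambda = 99.99² × 9 = 89,982. Power is about 1.00. Nine is only the smallest N that leaves an error df; power of 0.80 there would need f of about 17.4. The same floor arises with seven predictors and R² = 0.9999. The plan describes neither eight groups nor seven predictors.
- *Df as N − 2.* Nine follows by subtraction, but the power does not. For two groups of 4 and 5, 0.80 needs d of about 2.19 two-sided or 1.86 one-sided. At 99.99 power is about 1.00; at 0.9999 it is 0.25 or 0.38.

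**Step 4: if 0.9999 was meant and testing is two-sided, power at nine.** Paired t 0.75; exact Wilcoxon 0.68 (simulated, normal differences); Wilcoxon by ARE 0.66 to 0.72.

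**Step 5: precision at nine patients (exact Clopper-Pearson 95% intervals).** 0/9: 0 to 33.6%. 3/9: 7.5 to 70.1%. 9/9: 66.4 to 100%.

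**The case against.** The strongest reply is that the sentence contains a misprint rather than a faulty calculation. With 0.9999 in place of 99.99 and a one-sided Wilcoxon at the minimum ARE, N = 9, power 0.80 and df 6.78 (rounding to 7) all come back together, and Wilcoxon is a named test. This stands as a plausible origin. It still requires a hundredfold change to the printed effect and a one-sided test that the plan does not state, so it explains the sentence without making it correct.

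A second reply is that the plan never ties the calculation to the Friedman and Wilcoxon tests, that the association analyses could be its object, and that reference 36 may hold the basis. It is true that the link is not stated and that the source could not be consulted. But the sentence names no other test, and none of the N − 2 or F-test readings gives 0.80 power at nine with 99.99 or 0.9999.

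A reader might go further and infer that the trial is underpowered, or that nine is too few. The documents do not support this: taken literally, the printed effect needs fewer than nine for each planned test, and nine is stated only as a minimum. A power shortfall appears only if 0.9999 was meant and testing is two-sided, and the plan states neither.

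**Conclusion.** The sample-size statement is internally inconsistent as printed. For the named pre/post tests, an effect of 99.99 needs 2 to 6 cases, depending on the test, the sidedness and, for Friedman, the pattern of change; power at nine is about 1.00 against the stated 0.80. Among the readings tried, each route to nine needs something that the text does not state.

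The conclusion assumes that 99.99 is a standardised effect and that the calculation was meant for the planned tests. The power figures for 0.9999 further assume roughly normal differences and one observation per patient. Confidence is high that the figures do not agree as printed. The documents cannot show whether the cause is a misprint, incomplete reporting or the lack of a real calculation.

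**What to change.** Correct or withdraw the sentence.

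1. If a real calculation exists, replace 99.99 with the correct effect size and its metric. State the test, the outcome, the sidedness and what Df 7 refers to. If the planned test is two-sided, restate the power delivered at nine rather than a new N.
2. If none exists, withdraw the effect-size and 0.80 power claim and keep the original inputs in the change record. Report precision for the number actually analysed. Possible wording: *No formal power calculation supports the sample size. Proportions are reported per patient with exact 95% confidence intervals; for nine patients these are 0 to 33.6% for 0/9, 7.5 to 70.1% for 3/9, and 66.4 to 100% for 9/9.*

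The cost is one or two sentences in Patients and Methods and a line in the change record. No extra patients, visits or tests are asked for; the section already describes the recruitment period in the past tense. The downside is that the stated power and precision will look less favourable.
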